10.2.2. Visit 3 – Treatment 2 (Day 7-28)

The subject will return to the CRC 7 to 28 days after the first Treatment Visit. The procedures that will be repeated at Visit 3 are described in Section 10.2.1. Note that venous blood will be collected for a repeat of baseline hematology and serum chemistry assessments at Visit 3. At Visit 3, the subject will cross over to receive the other study drug, which will be administered at the time of Decision to Dose, so that each subject will have received one dose of G-Pen and one dose of GlucaGen Hypokit during the study. At the end of Visit 3, the subject will be asked to guess what their first treatment was, and what their second treatment was from the choices of “Xeris Glucagon, G-Pen, administered by auto-injector” or “Comparator Glucagon, GlucaGen Hypokit, administered by needle and syringe”. The subject’s responses will be recorded in the eCRF for the Subject Study Drug Assignment Questionnaire (see [Appendix 5](#)).

10.2.3. Visit 4 – Follow-Up (Day 9-35)

The subject will attend a Follow-Up Visit within 2 to 7 days after completing the final dosing visit or premature discontinuation. This visit will include the following assessments:

1. Review of changes in concomitant medications.
2. Physical examination, excluding breast, pelvic and genitourinary exams. To include review of injection sites to document any residual inflammation, pain or induration.
3. Body weight (no shoes, lightly clothed).
4. 12-lead ECG after 5-minute supine rest.
5. Vital signs after 5-minute seated rest.
6. Urine pregnancy test (females of child-bearing potential only).
7. Blood draws for complete metabolic count and complete blood count.
8. Solicitation of AEs by asking the subjects to respond to a non-leading question such as “how do you feel?”

In case of any premature discontinuation from the study, the subject will, if possible, be scheduled for a final follow-up visit.

10.3. Subject Withdrawal

Subjects may withdraw from the study at any time at their own request, or they may be withdrawn at any time at the discretion of the Investigator or Sponsor for safety, behavioral, or administrative reasons.

If a subject does not return for a scheduled visit, every effort should be made to contact the subject to determine the reason(s) why the subject failed to return for the scheduled visit, and to reschedule the missed visit. This includes contacting subjects, family members, or emergency

contacts via email and telephone. If such efforts fail, a certified letter should be sent to the subject's last known address requesting they contact study CRC.

In all circumstances, every effort should be made to document subject outcome, per the follow-up. Information regarding the reason for not completing the study will be recorded in the eCRF. The Investigator should inquire about the reason for withdrawal, request that the subject return for a Final Visit, and further follow-up with the subject regarding any unresolved AEs. It will be documented whether or not each subject completed the study. Any subject who receives at least one treatment dose of study drug will be included in the safety analysis.

If a decision by the Investigator or Sponsor is made to withdraw a subject, a Final Visit should be scheduled soon after the decision to withdraw is made. The subject will be asked to return to site for the assessments described in Section [10.2.3](#).

If the subject withdraws from the study and also withdraws consent, no further evaluations should be performed, and no additional data should be collected. The Sponsor may retain and continue to use any data collected before such withdrawal of consent.

Table 5 Schedule of Assessments

Assessment	Visit 1 Screening	Visit 2 Treatment 1	Visit 3 Treatment 2	Visit 4 Follow-up
	Day -30 to -3	Check-in: Day -1 Dose 1: Day 1	Target ¹ Check-in: Day 7 Dose 2: Day 8 (Dose 1 + 7-28 days)	Target ¹ Day 10-15 (Dose 2 + 2-7 days)
Informed consent	x	—	—	—
Medical history and demographics	x	—	—	—
Inclusion/exclusion review	x	—	—	—
Concomitant medications	x	x	x	x
Height, weight, and physical exam ²	x	—	—	x
12-lead ECG	x	—	—	x
Vital signs ³	x	x ³	x ³	x
Urine pregnancy test	x	x	x	x
Urine drug screen	x	—	—	—
Hematology & clinical chemistry	x	(x)	x	x
HbA1c and C-peptide	x	—	—	—
HIV, HCV and HBV	x	—	—	—
Gold scale for hypoglycemia unawareness	x			
Evening admission, dinner meal	—	x	x	—
Overnight fast and glucose monitoring from midnight	—	x	x	—
Hypoglycemia induction and confirmation of steady state	—	x	x	—
Randomization	—	x	—	—
Administration of study medication	—	x	x	—
Hypoglycemia Symptom questionnaire	—	x	x	—
Injection site discomfort scales	—	x	x	—

XSGP-304 Clinical Protocol
G-Pen (glucagon injection)

	Visit 1 Screening	Visit 2 Treatment 1	Visit 3 Treatment 2	Visit 4 Follow-up
Assessment	Day -30 to -3	Check-in: Day -1 Dose 1: Day 1	Target ¹ Check-in: Day 7 Dose 2: Day 8 (Dose 1 + 7-28 days)	Target ¹ Day 10-15 (Dose 2 + 2-7 days)
Draize scales for erythema/edema	—	x	x	—
Venous plasma glucose (PD) ⁴	—	X ⁵	X ⁵	—
Review AE(s)	—	x	x	x
Subject Study Drug Assignment Questionnaire	—	—	x	—

AE=adverse events, BP=blood pressure, ECG= electrocardiogram, HbA1c=glycated hemoglobin, HBV=hepatitis B virus, HCV=hepatitis C virus, HIV=human immunodeficiency virus, PD=pharmacodynamic, (X)=repeat if the visit is occurring outside of the allowed time window (i.e., more than 28 or 30 days have passed since the prior visit), YSI= Yellow Springs Instruments.

¹ Visit 3 should begin (i.e., admission to the CRC between 6 and 8 pm the day before treatment) 7 to 28 days after Visit 2; Visit 4 should occur 2 to 7 days after Visit 3.

² Excluding breast, pelvic and genitourinary exams. Note: height assessment is not required at Visit 4.

³ Temperature, respiration, heart rate and BP (after >5 min seated rest) will be performed at all visits.

Additionally, at visits 2 and 3, heart rate and BP will be repeated immediately prior to, and at 30, 60, 120, and 180 minutes post-dosing, with ±5 minutes for all procedures.

⁴ Via rapid glucose analyzer (YSI 2300 or 2900) before and during hypoglycemia induction, and every 5 minutes post study drug dose through 90 minutes, with ±2 minutes for all collections, and at 120, 150 and 180 minutes with ±5 minutes for collections.

⁵ If plasma glucose is > 350.0 mg/dL (>19.44 mmol/L) upon clinic arrival or if the plasma glucose the morning after the overnight stay is > 270.0 mg/dL (> 15.0 mmol/L) the visit should be rescheduled.

11. ASSESSMENTS

Every effort should be made to ensure that the required tests and procedures are completed as described. However, it is anticipated that there may be circumstances outside the control of the Investigator, who will take all steps necessary to ensure the safety and well-being of the subject. When a protocol-required test cannot be performed, the Investigator will document the reason(s) and any corrective and preventive actions taken to ensure that study processes are adhered to as soon as possible. The study team and the Sponsor will be informed of these incidents in a timely manner.

For all blood and urine collections, an effort should be made to obtain these samples at roughly the same time of day (i.e., morning or afternoon) across all visits as well as at the time periods specified in the Schedule of Assessments (Table 5). In addition, visits to the site must occur within the pre-defined windows outlined in this protocol; otherwise, they will be considered protocol deviations.

11.1. Blood Volume

There will be approximately 50 PD blood samples of approximately 2 mL drawn at each Treatment Visit for a total of about 100 mL of blood per visit. The two treatment visits will be 7 to 28 days apart. There will be 10.5 mL blood samples drawn at Screening, Visit 3 and at the Follow-up Visit for analysis of a clinical chemistry panel and hematology, with an additional 10.5 mL blood sample drawn at Screening for eligibility determination (HbA1c, C-peptide, and Serology). A total of approximately 250 mL of blood will be drawn over the duration of the study (Table 6).

Table 6 Frequency and Volume of Blood Collections

Sample Type	Sample Volume (mL)	Number of Sampling Times			Total Volume (mL)
		Screening Visit 1	Treatment Visits 2 & 3	Follow-Up Visit 4	
Clinical Chemistry	7.5	1	1-2 ^a	1	22.5-30
Hematology	3	1	1-2 ^a	1	9-12
HbA1c	3	1	-	-	3
C-peptide	2.5	1	-	-	2.5
Serology	5	1	-	-	5
PD ¹	2	-	~50/visit	-	200
Total	-	-	-	-	242-252.5

HbA1c=glycated hemoglobin, PD=pharmacodynamic, (a)perform at V3, perform at V2 only if the visit is occurring outside of the allowed time window (i.e., more than 30 days have passed since the prior visit),

¹ Plasma glucose measurements (1 to 2 mL each) at bedside via rapid glucose analyzer.

11.2. Clinical Laboratory Tests

The tests outlined in [Table 7](#) will be performed at the specified time points described in the Schedule of Activities.

Table 7 Clinical and Safety Related Laboratory Tests

Hematology	Chemistry	Urine	Laboratory
WBC count	Glucose	β -hCG ¹	HbA1c
RBC count	Creatinine	Drug screen ²	C-peptide
Hemoglobin	Na ⁺		HIVab
Hematocrit	K ⁺		HCVab
Platelet count	Ca ⁺⁺		HbsAg
	Albumin		
	Alkaline Phosphatase		
	AST		
	ALT		

ALT=alanine aminotransferase, AST=aspartate aminotransferase, β -hCG=beta-human chorionic gonadotrophin, HbA1c=glycated hemoglobin, HbsAg=hepatitis B surface antigen, HCVab=hepatitis C virus antibody, HIVab=human immunodeficiency virus antibody, RBC=red blood cell, WBC=white blood cell.

¹ Female participants of childbearing potential require a negative pregnancy test at Screening and prior to dosing for each of the 2 Treatment Visits. Pregnancy testing will be repeated as the Follow-up visit for safety reasons.

² Drug screening performed at Screening will include: cocaine, THC, opiates, amphetamines, methamphetamine, and phencyclidine. Analytes other than those listed above may be included in the test kits provided to the sites. Investigator will exercise discretion in allowing or excluding a subject from study participation based on a positive test for one of these analytes if the subject reports use of a concomitant medication that explains the result (e.g., positive urine test for opiates in a subject reporting use of cough syrup containing Dextromethorphan).. Except as noted below, continuation in the study requires all tests to be negative.

A central laboratory will be utilized for analysis of all blood analyses except for rapid plasma glucose measurements made during treatment visits. A procedures manual will be provided to each site by the central laboratory. This manual will cover procedures for the collection, processing and shipping of blood samples, and normal ranges for the central laboratory.

The central laboratory will provide sites with all supplies needed for collection, processing and shipping of all blood samples, as well as point-of-care urine pregnancy tests and rapid urine drug screen kits.

If a subject tests positive for a drug of abuse, the subject will normally be excluded from further study participation. However, if a subject reports use of a concomitant medication (prescription or over the counter [OTC]) that provides a reasonable explanation for a positive result (other than THC), the subject may be allowed to participate in the study at the Investigator's discretion. If the subject is not able to provide a reasonable explanation but still refutes a positive finding, a urine sample will be sent to the central laboratory for confirmation. The result of this confirmatory test will be considered definitive. The remainder of the Screening visit should still be completed in this case.

During treatment visits, plasma glucose concentrations will be measured using a bedside YSI rapid glucose analyzer model 2300 or 2900. At each time point specified in [Section 10](#), the results of both the black and white leads to one decimal place will be recorded in the source

documents, with the average of the two values rounded up to the nearest one decimal place accepted as the plasma glucose level for the time point as per the following examples.

Example #1: black lead=50.1 and white lead=49.8

Calculation: $50.1+49.8=99.9/2=49.95=50.0$ mg/dL recorded result

Example #2: black lead=74.4 and white lead=74.5

Calculation: $74.4+74.5=148.9/2=74.45=74.5$ mg/dL recorded result

The glucose analyzer will be set to auto-calibrate following the standard practice at each site. Before each subject visit, performance checks will be made as per the standard practice at each site, and sites will maintain a log of these results.

The EDC system implemented for this study will allow entry of plasma glucose values in either mg/dL or mmol/L. For reference, both units are provided in the written description and summary (Table 4) of the insulin dose adjustment algorithm. For reference, Table 8 provides a conversion chart for key values of plasma glucose referenced throughout the protocol.

Table 8 Conversion Table for Plasma Glucose Values

mg/dL	mmol/L
42.0	2.33
43.0	2.39
49.9	2.77
50.0	2.78
54.0	3.00
60.0	3.33
61.0	3.39
65.0	3.61
66.0	3.66
70.0	3.89
75.0	4.17
80.0	4.44
85.0	4.72
100	5.55
115.0	6.38
150.0	8.33
270.0	15.0
350.0	19.44

11.3. Electrocardiogram (12-lead ECG)

Single, supine 12-lead ECGs will be obtained at the pre-defined time-points outlined in the Schedule of Assessments (Table 5) as follows:

- 12-lead ECGs should be performed after the subject has rested quietly for at least 5 minutes in a supine position.

- 12-lead ECGs should be obtained before assessment of BP and heart rate, and prior to blood collections.

11.4. Blood Pressure and Heart Rate

The BP and heart rate will be measured at the times specified in the Schedule of Assessments (Table 5). Additional or changes to collection times, or collection of BP and heart rate using automated devices is permitted, as necessary, to ensure appropriate subject safety.

BP and heart rate will be measured in the seated position with the subject's arm supported at the level of the heart and recorded to the nearest mm Hg. The subject should be rested for at least 5 minutes before the BP is obtained. Measurements of both the BP and heart rate must be taken at least 2 minutes apart and recorded in the eCRF.

12. SAFETY AND ADVERSE EVENT (AE) REPORTING

12.1. Definition of an Adverse Event

An AE is any untoward medical occurrence in a clinical investigation subject administered a pharmaceutical product and which is not necessarily required to have a causal relationship with this treatment. An AE can therefore be any unfavorable and unintended sign, symptom, or disease temporally associated with the use of a medicinal product, whether or not considered related to the medicinal product. Examples of AEs include:

- Abnormal test findings.
- Clinically significant symptoms and signs.
- Changes in physical examination findings which are untoward and deemed clinically significant by the Investigator.
- Allergy/hypersensitivity.

The criteria for determining whether an abnormal objective test finding may be reported as an AE are as follows:

- Test result is associated with accompanying symptoms.
- Test result requires additional diagnostic testing or medical/surgical intervention.
- Test result leads to a change in study dosing or discontinuation from the study. significant additional concomitant drug treatment or other treatment.
- Test result is considered to be an AE by the Investigator or Sponsor.

Repeat of a test based on an abnormal result in the absence of the above conditions does not constitute an AE. Any abnormal test result determined to be an error does not require reporting as an AE.

A TEAE is an AE that either commenced following initiation of study treatment or was present prior to study treatment but increased in frequency or severity following initiation of study treatment.

Standard medical terminology should be used in describing AEs. Informal descriptions should be avoided.

12.2. Reporting Adverse Events

All observed or volunteered AEs regardless of treatment sequence or suspected causal relationship to the study treatment will be reported with two exceptions. Since it is being experimentally induced in this study, hypoglycemia will not be considered an AE in this study unless the event meets one of the definitions of a SAE (see Section 12.4). Injection site reactions will not be considered an AE unless a skin reaction or pain requires medical intervention.

For all AEs, the Investigator must pursue and attempt to obtain information adequate to determine the outcome of the AE and to assess whether it meets the FDA criteria for classification as an SAE, requiring immediate notification to Xeris.

For all AEs, follow-up by the Investigator is required until the event resolves or stabilizes at a level acceptable to the Investigator to consider it resolved. For unresolved AEs to be considered stable, the Xeris Medical Monitor must concur with that assessment.

As part of ongoing safety reviews conducted by the Sponsor, any non-SAE that is determined to be serious (according to the FDA definitions of an SAE) will be reported by the Sponsor as an SAE. To assist in the determination of case seriousness, further information may be requested from the Investigator to provide clarity and understanding of the event in the context of the clinical study.

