After 180 minutes posttreatment, subjects will resume insulin pump therapy, if applicable, and will be given a meal. Subject may be discharged after 180 minutes posttreatment if their plasma glucose is > 100 mg/dL (5.56 mmol/L) and if medically stable. At the Investigator’s discretion, subjects’ prescribed insulin regimen can be restarted, or the meal can be given sooner, but not earlier than 90 minutes post-glucagon treatment, to prevent hyperglycemia or rebound hypoglycemia.

After a wash-out period of 7 to 28 days, subjects will return to the CRC and the study procedures will be repeated with each subject crossed over to the other treatment. After study-related procedures are performed on each of the treatment days, subjects will be discharged. A Follow-Up Visit will be

XSGP-304 Clinical Protocol
G-Pen (glucagon injection)

	
conducted 2 to 7 days after administration of the final dose of study drug as a safety check.
 
Tolerability will be assessed by comparing AE reports between the G-Pen and GlucaGen Hypokit treatment groups. In addition, at the end of each treatment period the subjects will complete questionnaires to assess injection site discomfort, and the Investigator will use a modified Draize scale to evaluate the injection sites after each administration.

Data management and statistical analysis:	
Data will be entered into an electronic Case Report Form (eCRF) by the study site personnel. Data will be monitored at on-site visits by Xeris personnel or by a contract research organization (CRO) delegated by Xeris. A stand-alone Statistical Analysis Plan (SAP) will be written to detail all protocol specified analyses. The SAP will take precedence over the protocol. The primary endpoint will be analyzed using an exact test procedure based on the conditional distribution for a maximum clinically acceptable non-inferior margin of $\leq 5\%$.

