Plasma glucose levels will be monitored for 180 minutes post-dosing. It is believed that plasma glucose < 54 mg/dL (< 3 mmol/L) will be low enough to generate neuroglycopenic and autonomic symptoms in most subjects, yet high enough (i.e., > 42 mg/dL [> 2.33 mmol/L])) to avoid the impairment of consciousness. Consequently, subjects will complete a questionnaire about symptoms of hypoglycemia [Nerموen] during the hypoglycemia induction phase, and for 180 minutes after treatment with glucagon.

After a wash-out period of 7 to 28 days, subjects will return to the CRC and the procedure will be repeated with each subject crossed over to the other treatment.

After study-related procedures are performed on each of the treatment days (see Table 5), subjects will be discharged after consuming a meal as per each site's usual practice. A follow-up visit as a safety check will be conducted 2 to 7 days after administration of the final dose of study drug.

The last subject last visit (LSLV) for each site is defined as the date the last subject completes the Follow-Up Visit (Visit 4), with the understanding that final review by the Investigator may be delayed a few days to allow for receipt of final lab results. The end of the trial is the date of the LSLV for the last site.

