5. Subcutaneous administration of the study drug will be made to the abdomen around the umbilicus as per [Section 9.3.3](#). Clock time of study drug administration will be recorded in the source documents. After study drug injection, the study product will be disposed in a location away from the subject in a manner that maintains the blind. After disposal, the blindfold and headphones will be removed from the subject.
6. Following study drug administration, plasma glucose will be measured every 5 ± 2 minutes through 90 minutes, and every 30 ± 2 minutes thereafter through 180 minutes post-dosing.

7. At 180 minutes post-dosing, the subject will resume insulin therapy and be given a meal as per the standard practice at each site. The subject can be discharged from the clinic if their plasma glucose is >100 mg/dL (> 5.55 mmol/L) and the subject is deemed medically stable.
8. After study drug administration and before 180 minutes post-dosing, if rising glucose levels are observed and if deemed medically necessary, insulin therapy or other medical intervention may be initiated by the Investigator.
 - a. Such intervention is not recommended to occur before 90 minutes post-dosing of study drug.
 - b. Plasma glucose data and assessments of neuroglycopenic symptoms will be censored after the time of intervention, per the statistical analysis plan.
 - c. These interventions (such as insulin, carbohydrates, or a meal) prior to 180 minutes post study drug administration should be captured in the source documents, and further glucose measurements may be performed at the discretion of the Investigator.

Hypoglycemia Symptom Assessments

Subjects will complete a questionnaire regarding severity of hypoglycemia symptoms ([Appendix 1](#)) at the following time points:

1. Just before the IV bolus push dose of insulin is given at the start of the hypoglycemia induction procedure (baseline),
2. Every time blood is drawn for evaluation of plasma glucose concentration during the induction procedure,
3. Just before study drug is administered,
4. Every 5 ± 2 minutes after glucagon is administered until 90 minutes post-dosing, and every 30 minutes (coinciding with plasma glucose measurements) between 90 and 180 minutes post study drug administration.

Local Tolerability and Adverse Events

Local tolerability and AEs will be assessed as follows:

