12.3. Reporting Period

For all AEs, the reporting period to Xeris begins from the subject providing informed consent, through the Follow-up Visit. All adverse events will be followed until resolution or the subject is medically stable.

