5.3.6.2 Secondary Endpoints

5.3.6.2.1 Pharmacodynamic (PD) Parameters

The PD endpoints will be derived from the individual glucose profiles. Pharmacodynamic characteristics, including:

- AUC_{0-90} and AUC_{0-180} : plasma glucose area under the concentration versus time curve for 90 and 180 mins from glucagon administration;
- C_{max} : Maximum concentration of glucose in plasma;
- T_{max} : time (in mins) when Glucose C_{max} is reached;

The following rules will be used for incomplete data:

- AUC: If there are missing data points before the last observed value, they will be extrapolated using the last two data points;
- AUC: If there are missing data points after the last observed value, they will not be imputed, and the AUC will be treated as not defined;
- If insulin starts after receiving glucagon, the glucose values post insulin start will be censored out and considered as missing. This is also considered a major protocol deviation.

Comparison between the treatments will be performed using a mixed model with treatment, period and treatment*period as fixed factors and subject as a random factor.

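### Non-serious hypoglycemia is exempt from AE reporting from consent to Follow-up, so a fall back after rescue is missing from the by-drug AE comparison

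*Protocol*

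**What the plan says.** Protocol 12.2 asks for all AEs whatever their suspected cause, with two exceptions. The first concerns hypoglycemia. Its reason is "Since it is being experimentally induced in this study" and its rule is that "hypoglycemia will not be considered an AE in this study unless the event meets one of the definitions of a SAE". No time limit or link to the induction window is attached. The second concerns injection site reactions, which do become AEs if they need medical intervention.

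Protocol 12.3 says that for all AEs "the reporting period to Xeris begins from the subject providing informed consent, through the Follow-up Visit". Among the grounds on which Protocol 12.1 lets an abnormal result be reported as an AE is "Test result requires additional diagnostic testing or medical/surgical intervention".

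The Protocol Synopsis lets the investigator restart insulin or bring the meal forward, no earlier than 90 minutes after glucagon, "to prevent hyperglycemia or rebound hypoglycemia". Protocol 7.1 states: "Plasma glucose levels will be monitored for 180 minutes post-dosing". Protocol 10.2.1.2 (Day 1, preparation and administration of study drug, item 8) adds: "Plasma glucose data and assessments of neuroglycopenic symptoms will be censored after the time of intervention, per the statistical analysis plan". It names insulin, carbohydrates and a meal as interventions, and leaves further glucose sampling to the investigator. SAP 5.3.6.2.1 names insulin only: "the glucose values post insulin start will be censored out and considered as missing".

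The safety analysis in Protocol 13.5 and the safety variables in SAP 5.3.6.3 neither narrow the exemption nor add a hypoglycemia measure.

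**The concern.** The reason fits the episode that the investigators create. It stops fitting once that episode has been reversed, but the exemption continues. Hypoglycemia that returns after rescue is not deliberately induced, could differ between the two products, and bears on whether the rescue holds.

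The secondary objective is comparative safety and tolerability. For non-serious recurrence, the AE tables will show none on either drug because of the rule, whatever happened. A reader of the study report could take that for evidence of no difference.

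The second exemption in 12.2 is built more carefully. Injection site reactions return to AE status when they need intervention, and they have their own by-treatment measures (VAS and Draize). Non-serious hypoglycemia has neither safeguard.

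**Working it through.** The point concerns a definition, so the plan states no figure to reproduce. The check has four parts.

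**1. Time covered by the rule against time covered by its reason**
- Reporting window: screening to Day 1 is 3 to 30 days (Protocol 10.1), dose 1 to dose 2 is 7 to 28 days (10.2.2), and dose 2 to Follow-up is 2 to 7 days (10.2.3). Shortest: 3 + 7 + 2 = 12 days. Longest: 30 + 28 + 7 = 65 days.
- Induction: about 2 to 3 hours each (9.3.3), with two needed and at most four allowed (7.2). Shortest: 2 × 2 = 4 h. Longest: 4 × 3 = 12 h.
- Share: from 4 / (65 × 24) = 0.3% to 12 / (12 × 24) = 4.2%.
- Section 9.3.3 counts from randomization, which 10.2.1.2 places 30 to 60 minutes into induction. Adding a full hour each time raises the upper limit to 16 / 288 = 5.6%.

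**2. Would any planned output count a fall back after response?**
- Primary endpoint and time to response (SAP 5.3.6.1, 5.3.6.2.3): these record the first success only.
- AUC, Cmax, Tmax and mean curves (SAP 5.3.6.2.1, 6.6.2): these do not count individual relapses.
- Yes/no question on feeling hypoglycemic (SAP 5.3.6.2.2): the categories include No at baseline then Yes, and Yes at baseline never followed by No. Recurrence in the order Yes, No, Yes falls in no category. Time to resolution stops at the first No.
- Glucose listing 16.2.6.1.1, individual glucose curves and symptom scores by timepoint (SAP 6.6.3, Appendix 1): a fall within 180 minutes could be seen here, but it is not counted.
- Serious TEAE and SAE summaries (SAP 5.3.6.3): these capture hypoglycemia meeting an SAE definition.

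**3. Where the induced episode ends**
- Dosing requires plasma glucose of at least 42 and below 54 mg/dL. A 20 mg/dL rise counts as a response under SAP 5.3.6.1.
- From 42 the response can occur at 42 + 20 = 62 mg/dL, and from 50 at 50 + 20 = 70 mg/dL. A subject starting between 42 and 50 can therefore respond while still at or below 70 mg/dL, within the same induced episode. A positive response is too early an end point for the exemption.

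**4. Scale**
- Background: Protocol 6.1.1 gives two symptomatic events per week. Over 12 to 65 days that is 2 × 12/7 = 3.4 to 2 × 65/7 = 18.6 per subject, or about 418 to 2,266 in 122 subjects. Most are unrelated to study drug.
- In an assumed 24-hour window after each dose: 122 × 2/7 = about 35 background episodes per drug.
- Severe background, at about one a year (6.1.1), from dose 1 to Follow-up (9 to 35 days): 122 × 9/365 = 3 to 122 × 35/365 = 12 events.
- Attribution periods (SAP 5.2): about 7 to 28 days after dose 1 and 2 to 7 days after dose 2. At two events per week these would hold 244 to 976 and 70 to 244 background episodes.
- Chance of at least one rebound case on a drug given to 122 subjects, 1 − (1 − p)^122: p = 1% gives 71%, 2% gives 91%, and 5% gives 99.8%. These rates are assumptions.

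**The case against.** The strongest reply is that little of importance is lost. Protocol 12.4 goes beyond hospitalization: events that may need intervention to prevent a serious outcome should usually be treated as serious, and sponsor review under 12.2 can upgrade a case. Glucose is sampled every 5 minutes to 90 minutes and then every 30 minutes to 180, and the values are listed and plotted by drug. Insulin infusion is stopped before dosing, and discharge requires glucose above 100 mg/dL. The summaries of earlier studies in Protocol 6.4 mention no rebound hypoglycemia.

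Much of this stands, and it rules out three stronger readings:
- A reader might infer that hypoglycemia never reaches the safety comparison. It does when it meets an SAE definition.
- A reader might infer that no planned output would show a recurrence. Listings, individual curves and timepoint summaries could, within 180 minutes and before any intervention.
- A reader might infer that G-Pen is expected to cause more rebound. The documents give neither a rate nor a difference between drugs.

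The gap for non-serious events remains. The glucose data are handled as pharmacodynamic data, with no count of recurrence. Nor is the full 180 minutes assured. After an intervention the data are censored and sampling is discretionary, and the local tolerability text of 10.2.1.2 foresees measurements stopping after 90 minutes. Item 8 opens with rising glucose, but its list includes carbohydrates and meals. I read it as also reaching a subject fed because glucose was falling, whose later values could then be lost.

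**Conclusion.** The point holds in a limited form. Non-serious hypoglycemia is exempt for the whole reporting period, while the stated reason applies to roughly 5% of that period or less. Non-serious recurrence after rescue, which the Synopsis anticipates, is absent from the by-drug AE comparison. Only SAE-level events and uncounted 180-minute data would show it.

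The primary and secondary efficacy analyses are unaffected. How many events would be missed cannot be stated, because the documents give no rebound rate. Under the assumed 1% to 5% per subject, at least one case in 122 is likely to near certain. This is worth correcting because it touches the secondary objective and costs little.

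**What to change.** **Protocol 12.2.** Limit the exemption to the induced episode: from the start of induction until plasma glucose has first recovered above 70 mg/dL (a 20 mg/dL rise alone is not enough) or other glucose treatment has been given. Record later hypoglycemia up to discharge under the ordinary AE rules. State separately that non-serious episodes before induction or outside the treatment visits stay exempt as background. Otherwise the narrower wording would bring in the hundreds of home episodes estimated above.

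**SAP 5.3.6.3 and Appendix 1.** Add one descriptive by-drug table of subjects whose plasma glucose, after first exceeding 70 mg/dL, falls back to 70 mg/dL or below, and to below 54 mg/dL, through 180 minutes. Use all recorded values, including the last before any intervention. Show alongside, by drug, the number given carbohydrate, a meal or insulin before 180 minutes, so that losses to censoring are visible.

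**Optional.** If episodes needing another person's help are also recorded after discharge, compare them only in one fixed post-dose window of equal length in both periods. The SAP's attribution periods are unequal, and background severe events would otherwise dominate. These events would rest on subject report.

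Both cut-offs already appear in the protocol. Here they serve reporting only and change no treatment rule. The cost is a short change to 12.2, one extra table and a few more AE entries. The table uses samples already scheduled, but will be incomplete where sampling stopped early.
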